**Comparison of Operating Room Time Length with the Use of Virtual Surgical Planning Versus
Conventional Treatment of Mandible Fractures**

NCT04283981

Version Date: 02/10/2021

Protocol Title:	Comparison of Operating Room Time Length with the Use of Virtual Surgical Planning Versus Conventional Treatment of Mandible Fractures
Principal Investigator:	[name] [name]
UTHealth Co-Investigators:	[name] DDS MD FACS; [name] DDS MD PhD FACS; [name] DDS; [name] MD; [name] DDS; [name] DDS
Study Coordinators:	[name]; [name] APRN FNP; [name]
Population:	All patients presenting with diagnosed mandible fracture at Memorial Hermann Hospital
Number of Sites:	Memorial Hermann Hospital
Study Duration:	Between November 2019 and November 2021 (until adequate data is obtained for significant statistical analysis)
Subject Duration:	From the initial preoperative evaluation to end of treatment which is 2 months

General Information

Patients at Memorial Hermann Hospital who have an isolated mandibular fracture and who are appropriately consented will partake in this study. They will be split evenly into 2 groups which are virtual surgical planning (VSP) and the conventional surgery. The conventional surgery involves having medical grade CT in order to assess the mandible fracture and having an open reduction and internal fixation of the fracture. The reconstruction plate will be bent intra-operatively. VSP patients will also receive the medical grade CT and also receive intraoral scans for aid in assessing occlusion. 3D models of the patient's jaws will be made and set into the proper occlusion. A reconstruction plate will be bent before the surgery using these models to be used at the time of surgery. Advancements in VSP technology increasingly demonstrate improvements in operative efficiency and reduce operating time. Pre-surgical planning and fabricated guides can potentially improve intraoperative efficiency, postoperative outcomes, and minimize complications. Additionally, use of this technology may permit a reduction of operating costs associated with longer operating room and anesthesia times in conventional treatments. Another challenge presented with VSP is turn over time from the actual planning and fabrication of splints or anatomical models to having them ready for surgery. This can take between one to two weeks and delay treatment for acute trauma cases.

Objectives

Objective of this randomized controlled study is to compare operating room time between conventional treatment techniques (without VSP) versus use of VSP and surgically-guided techniques. Surgically-guided techniques will include use of an occlusal splint (from digital intraoral scanner), and a 3D printed anatomical model for adaptation of pre-bent titanium plates. Additionally we will determine if remotely printing anatomical guides and splints is feasible and can decrease turn over time for VSP.

OBJECTIVES	ENDPOINTS	JUSTIFICATION FOR ENDPOINTS
Primary		
To compare OR time between conventional treatment techniques (without VSP) vs use of VSP and surgically guided techniques	ORIF time, which is defined as starting after the dissection is complete and fractures are reduced until final screws are placed. Ideally the dissection, reduction, closure	To compare whether or not the intervention (VSP) yielded decrease OR time

OBJECTIVES	ENDPOINTS	JUSTIFICATION FOR ENDPOINTS
	should not change from the control to the treatment	
Secondary		
To compare and contrast the effect of any other variables that might have an effect on the overall result	Age, gender, fracture pattern, Type of archbars, fit guides, type of approach, Surgical revisions, infections, mouth opening, Hardware failure defined as plate fracture or screw loosening	Age, gender, and fracture pattern is basic data needed to analyze results. The rest of the endpoints are important because they might possibly have an effect on the primary objective.

Background Information

Mandibular fractures are the second most common facial bone fracture [1] due to its prominent position in the maxillofacial region and the mandible's relative lack of structural support. The most common cause of injury is low impact blunt trauma, including motor vehicle accidents (MVCs), physical assault, and sports injuries [1, 2]. Advancement in mandibular reconstruction increasingly allow for interventions that result in reduction of facial deformities [3]. With the application of virtual surgical planning (VSP), the planning process has become more precise, reducing the number of intra- and postoperative complications [4-16].

Complex mandibular fractures often require open treatment with internal fixation of the mandibular segments, and maxillomandibular fixation for proper healing. Treatment and surgical approaches vary with fracture patterns, location, degree of bony displacement, and involvement of dental structures. Greatly displaced fractures, fractures in difficult anatomical locations, and loss of dental landmarks (occlusion) can pose a challenge for the reconstructing surgeon. [1, 3, 4]. Successful management of these complex fractures requires careful consideration of these factors. Such challenges may include achieving an accurate reduction of the fragments and placing a stable reconstruction plate for the purpose of re-establishing the original shape of the mandible. In order to help overcome these challenges, VSP has been utilized for the reconstruction of traumatic facial injuries, including the repair of complex mandible fractures. Three-dimensional modeling of maxillofacial injuries facilitates precise intraoperative reduction of displaced bone fragments, while CAD/CAM technology produces occlusal splints that allow superior restoration of facial symmetry, appearance, and function to those fitted intra-operatively [5].

The advent of VSP allows surgeons to increase surgical precision while reducing operating time. In addition to shortening OR time, surgical reconstruction of the mandible using VSP and pre-bent hardware demonstrates successful restoration of orofacial contour and function [4, 7, 8, 10, 14]. Today, there are numerous publications on the use of VSP and 3D imaging methods to fabricate occlusal splints and anatomical models to facilitate adaptation of a pre-bent reconstruction plate for mandibular reconstruction [4-23]. Furthermore, these studies have demonstrated reduction in operating time and had minimal intraoperative plate manipulation [4-16].

Excellent results have been shown for VSP on mandibular reconstruction with assistance from an intraoral scanner for modeling generated occlusal splints and pre-bent fixation plates. This randomized control study will attempt to determine whether there is reduction in operating time, costs, and post-operative complications. This treatment modality may potentially allow for increased accuracy, efficiency, and outcome in this surgical setting. A reduced time in the operating room could potentially lead to better outcomes for the patient while decreasing overall treatment cost. Hence, a decreased operating time, anesthesia time, and hospitalization could thereby, potentially, justify the additional preoperative costs that come with computer assisted surgical planning. Furthermore we will determine the effectiveness of remote 3D printing guides and models to decrease the turn over time of VSP.

Study Design

- In this randomized controlled study, we will evaluate patients from the University of Texas Health Science Center at Houston, Department of Oral & Maxillofacial Surgery treatment facility at Memorial Hermann Hospital

- from a patient population that undergoes mandibular trauma via open reduction internal fixation (ORIF) via intraoral or extraoral approach, using an intra-oral scanner, VSP® 3D Systems, and Stryker Anatomical Models.
- The study population will be composed of patients presenting with mandible fractures to Memorial Hermann Texas Medical Center in Houston, Texas from November 2019 to November 2021 (until adequate data is obtained for significant statistical analysis).
- Recruited and consented patients will be asked to attend the follow up appointments, for permission to review their records, to answer additional questionnaires, and have additional measurements/formal exam taken.
- Subjects will be re-evaluated at 3 within 6 weeks to assess the patient's mandible fracture healing via panorex or maxillofacial CT (follow ups: 1 week, 3 weeks +/- 1 week, 6 weeks +/- 1 week)
- Patients will be recruited from the Memorial Hermann Hospital when assessed and scheduled for mandibular reconstruction via open reduction internal fixation with VSP, fabrication of occlusal splint (from intraoral scanner), and 3D printed anatomical model for adaptation of pre-bent reconstruction plate.
- The study design would implement a randomized non-blinded clinical trial. Randomization will be performed by having sealed envelopes at the time of enrollment with either "original" or "VSP" written on cards.
- Both groups of patients will be treated by a team of oral and maxillofacial surgery residents and attending surgeons.
- The patients will be divided into two groups, the treatment group and control group. Records for both groups will be evaluated by the investigators and the patients will be asked to follow up in the OMFS Clinic at Memorial Hermann and treated by the Oral & Maxillofacial Surgery service.
 - The treatment group corresponds to patients undergoing mandibular reconstruction via open reduction internal fixation (intraoral or extraoral approach) utilizing virtual surgical planning via 3D Systems, bite registration and fabrication of occlusal splint via intraoral digital scanner, and mandibular hardware
 - The control group will include patients that undergo mandibular reconstruction via open reduction internal fixation (intraoral or extraoral approach) in standard fashion (without virtual surgical planning assistance and occlusal splint)

Study Population

Our study population consists of all patients with complex mandible fractures presenting to the University of Texas Health Science Center at Houston, Department of Oral & Maxillofacial Surgery facility at Memorial Hermann Hospital between October 2019 and October 2021 (until adequate data is obtained for significant statistical analysis).

- We anticipate recruitment of approximately 50 patients (25 patients for each control and treatment group) from Memorial Hermann Hospital. The control group will undergo mandibular fixation via standard open reduction internal fixation techniques. The VSP group will undergo mandibular fixation with standard open reduction internal fixation techniques and utilization of intraoperative occlusal splint, Virtual Surgical Planning via 3D Systems, and Stryker Anatomical Models.
- Inclusion criteria:
 - Patient consent
 - Male or female; 18 years or older
 - Complex mandible fracture (at least two fractures) that require ORIF of at least one fracture.
- Exclusion criteria:
 - Patient refusal to participate in study
 - Infected mandible fracture
 - Closed reduction treatment of mandible fracture
 - Fractures older than 2-3 weeks at the time of treatment
 -
 - Other etiologies than trauma of the mandibular fracture or pathologic fracture secondary to benign or malignant pathology that may require resection
 - Pregnant patients will NOT be excluded from the study
 - Co-morbidities (auto-immune disease, osteoporosis, titanium or metal allergy, uncontrolled diabetes (A1c greater than 8)

Patient would be enrolled upon evaluation and consent for mandibular reconstruction at the University of Texas Health Science Center at Houston, Department of Oral & Maxillofacial Surgery treatment facility at Memorial Hermann Hospital - Texas Medical Center

Study Procedures

- No additional time will be required from participants than the time required for the normal care, treatments, or management. Patients will not be charged anything additional to participate in the study and will also not receive any compensation.
- Patients will have post-operative CT scan to ensure adequate reduction and fixation of fractures
- Patients will be re-evaluated at 3 follow up visits within 6 weeks to determine mandible fracture healing.
 - Post-op (prior to discharge), 1 week, 3 weeks +/- 1 week, 6 weeks +/- 1 week
- Collected data will include:
 - Age, gender, operating time (ORIF time, total operating time), fracture pattern
 - ORIF time will be defined as starting after the dissection is complete and fractures are reduced until final screws are placed.
 - Ideally the dissection, reduction, closure should not change from the control to the treatment
 - Accuracy of fracture reduction
 - Type of archbars, fit of guides, type of approach
 - Surgical revisions, infections, mouth opening
 - Hardware failure defined as plate fracture or screw loosening
- Once data is collected, variability will be calculated within individual test results.

Data & Safety Monitoring

- Adverse events
 - Expected adverse events: pain, infection, bleeding, swelling, trismus, possible nerve damage, damage to adjacent structures
 - Unexpected adverse events: repeat fractures, trauma post-surgery, plate fractures, loose screws, mal-unions, non-unions, poor cosmetic outcome, delayed healing
 - Potential serious adverse events: sepsis from infection, osteomyelitis
- Unanticipated problems will be discussed amongst investigators.
- Methods of measuring results will be discussed amongst investigators and standardized so that measurements remain consistent from investigator to investigator.
- The research team will periodically review its protocols to ensure maximal patient safety and data validity.

Statistics

- Generalized linear model will be used to identify data distribution differences between the two study groups.
- This data will be recorded using a standardized data sheet to be shared within the department.
- Power analysis was performed for an f-test, and to show a large effect size ($f=0.4$) between the groups will require:
 - $n = 25$ patients/group to achieve a power of 0.8 and a significant level of 0.05.
- **ANOVA-based power analysis figures require:**
 - $n = 26$ patients/group for a large effect size
 - $n = 64$ patients/group for a medium effect size
 - $n = 393$ patients/group for a small effect size

Ethics

- A written informed consent will be obtained from the adult subject. This site has submitted the consent documents for CPHS review.
- IRB approval will be sought from CPHS (Committee for the Protection of Human Subjects).
- Treatment and clinical management will not be affected by this study. The surgical procedure investigated in this study is considered standard of care.
- Informed consent for the review of records and permission to conduct additional questionnaires and measurements at each follow up appointment will be obtained from each patient prior to commencing the study.
- To protect the privacy of subjects, only members of the research staff including the attending doctors, residents, will have access to patient health information

Data Handling & Record Keeping

- Data collected electronically through the medical record system and recorded on the data sheets attached to this protocol. Access to source documents will be per respective EHR guidelines on computers that are encrypted, and password protected. The data sheets, including consents, will be kept with the principal investigator in a locked cabinet. The patients will also receive a copy of their consent forms. HIPAA compliance guidelines will always be used.
- Human subjects will not be directly identifiable, but only identifiable in the study database through identifying information (Hospital MRN)
- Age of patient will be recorded to replace birth date. Only specific disease information, sex, and age as potential identifier will be used. No identifiable patient name, number or birth date will be used in this study and subsequent publications.

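### The only named model has no covariate: adjust ORIF time for fracture pattern, and list postoperative complications as outcomes, not as influences on ORIF time

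*Combined protocol and SAP*

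**What the plan says.** **Primary endpoint (Objectives table, primary row).** "ORIF time, which is defined as starting after the dissection is complete and fractures are reduced until final screws are placed". The interval lies wholly within the operation.

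**Secondary objective and endpoints (same table, secondary row).** The objective is "To compare and contrast the effect of any other variables that might have an effect on the overall result". The endpoints are age, gender and fracture pattern, followed by "Type of archbars, fit guides, type of approach, Surgical revisions, infections, mouth opening, Hardware failure defined as plate fracture or screw loosening". The justification column has two sentences. The first says that age, gender and fracture pattern are basic information required for analysing the results. The second covers everything else: "The rest of the endpoints are important because they might possibly have an effect on the primary objective".

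**Background Information.** On fracture pattern: "Treatment and surgical approaches vary with fracture patterns, location, degree of bony displacement, and involvement of dental structures". On complications: "This randomized control study will attempt to determine whether there is reduction in operating time, costs, and post-operative complications".

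**Statistics.** One sentence names a model: a generalized linear model for differences between the two groups. It gives no outcome, family, link, covariate or time point. The sample size comes from an F-test with f = 0.4, power 0.8 and a 0.05 level, giving 25 per group. A second list gives 26 for the same effect size.

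**Study Procedures.** Archbars, fit of guides and approach are on one line of the data list, and revisions, infections and mouth opening on another. Follow-up runs from before discharge to 6 weeks, plus or minus 1 week.

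**The concern.** Two matters are left open, both about what role a variable plays.

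The first is adjustment. Fracture pattern is fixed before randomisation, is recorded for every patient, and is said to drive how the patient is treated. It is therefore a natural covariate for operating time. The plan neither includes nor excludes it. At stake is the precision of the primary comparison in a trial of about 50 patients. Because the trial is not blinded, fixing the model in advance also stops it being chosen once the data are seen.

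The second is the secondary list. One reason, a possible effect on the primary objective, is given for two kinds of item. It fits archbars, approach and, in the VSP arm, fit of guides. It does not fit a revision, infection or hardware failure found during follow-up, because the ORIF clock stopped at the final screws. The Background asks whether VSP reduces complications, which makes them outcomes. A reader cannot tell which comparison will be reported.

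**Working it through.** **Inputs from the plan.** f = 0.4, two-sided 0.05 (a two-group F-test), 25 per arm, total N = 50. For two equal groups d = 2f = 0.8 within-arm SD.

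**Assumptions.** R², the share of within-arm variance in ORIF time explained by fracture pattern, is not in the documents; 0%, 10% and 20% are shown. Normal errors are assumed, as in the plan's own F-test.

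**Reproducing the plan's figure.**
- Normal approximation: 2 × (1.960 + 0.842)² / 0.8² = 24.5, rounded up to 25.
- Noncentral F: λ = n d² / 2 = 25 × 0.64 / 2 = 8.00 on 1 and 48 df gives power 0.791. At 26 per arm λ = 8.32 and power is 0.807.

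Both 25 and 26 are thus reproduced, by two methods. The calculation is for an unadjusted comparison.

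**Adding k fracture-pattern terms.** Adjustment divides the residual variance by 1/(1 − R²). It costs k df and a small loss from chance imbalance, on average k/(N − 1) = k/49 of the information:

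λ = 8.00 × (1 − k/49) / (1 − R²), on 1 and 48 − k df.

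| Assumed R² | One term: λ | Power | Two terms: λ | Power |
|---|---|---|---|---|
| 0% | 7.84 | 0.783 | 7.67 | 0.774 |
| 10% | 8.71 | 0.824 | 8.53 | 0.816 |
| 20% | 9.80 | 0.865 | 9.59 | 0.858 |

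Simulations with binary covariates left to chance imbalance agree: one term 0.783 to 0.784, 0.822 to 0.824 and 0.865 to 0.866; two terms 0.772 to 0.775, 0.814 to 0.815 and 0.858 to 0.860. Type I error was 0.050 to 0.051.

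**Break-even.** Ignoring the lost df, adjustment pays once R² exceeds k/49: about 2% for one term and 4% for two.

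**Equivalent sample size.** Dividing λ by d²/2 = 0.32, one term at R² 10% is worth 8.71 / 0.32 = 27 per arm unadjusted, and at R² 20%, 9.80 / 0.32 = 31 per arm.

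**Timing of the secondary items.**
- Fracture pattern: before randomisation, so eligible as a covariate.
- Archbars, approach, fit of guides: settled before or during surgery, so they may relate to ORIF time. Guides belong to the VSP arm, so their fit has no counterpart in controls.
- Revisions, infections, hardware failure found at follow-up: after ORIF time has ended, so they can only be outcomes.

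**What 25 per arm can say about complications.** With assumed counts of 2/25 on VSP and 5/25 on control, the risk difference is 0.08 − 0.20 = −12 percentage points, with a Newcombe 95% interval of −32 to +8. With 1/25 and 3/25 it is −8 points (−26 to +9). These would be estimates, and an interval that includes zero would not show equal risk.

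**The case against.** The strongest reply is that nothing invalid has been planned. Randomisation makes the unadjusted comparison valid, and the sample size was computed for exactly that. This stands: the point is about precision, not bias.

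A second reply is that the plan already points to using fracture pattern, since the Objectives table calls it necessary to the analysis. That sentence does hint at a role, but it does not say whether fracture pattern is a covariate, a subgroup or a descriptive item, and the Statistics section does not take it up.

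Three stronger readings are tempting, and the documents do not support them.

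- *The primary comparison will be biased because postoperative events will be put in the ORIF-time model.* No section says they will. The sentence at issue stands in a justification column and specifies no model, so there is no planned bias to quantify.
- *There is no method for comparing complications.* The generalized linear model sentence is not limited to ORIF time and could cover binary outcomes. What is missing is specification, not a method.
- *Revisions and hardware failure could never affect ORIF time.* The plan does not time them. A screw that loosened and was replaced before the final screws were placed would lengthen ORIF time. The argument is safe only for events found during follow-up.

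**Conclusion.** The point holds, as an improvement that should be made rather than a flaw that invalidates the trial. The primary comparison can be made more precise with data already collected. Power at 25 per arm rises from 0.79 to about 0.82 or 0.865 with one term, if fracture pattern explains 10% or 20% of the variance in ORIF time. The downside if it explains nothing is about 0.01 for one term and 0.02 for two. These figures rest on the plan's f = 0.4 and on assumed R² values; the documents give no R², only the statement that treatment and approach vary with fracture pattern. The stated sample size is unaffected.

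On the secondary list, the shared justification does not suit complications found at follow-up and sits badly with the Background. The remedy there is a clear assignment of roles. It does not rest on any demonstrated error in the primary result.

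**What to change.** 1. **Statistics.** State that the primary analysis is ORIF time on randomised arm plus one or two fracture-pattern terms, named before analysis (for example two versus three or more fractures). Take them from the preoperative data; both arms have the CT, since "VSP patients will also receive the medical grade CT and also receive intraoral scans for aid in assessing occlusion". State that the arm comparison will not be adjusted for variables determined after randomisation.
2. **Objectives, secondary row.** List revisions, infections and hardware failure as secondary outcomes compared by arm over the existing 6-week follow-up, each as a risk difference with a 95% confidence interval.
3. **Same row.** Keep archbars and approach as descriptive factors. Describe fit of guides in the VSP arm only.

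**Cost.** Wording in two sections, and one or two fields coded for about 50 patients from information already held. No extra visit or additional reader is needed. Recruitment is dated from November 2019 and this document carries "Version Date: 02/10/2021", so some patients may already have been randomised. Their terms can be taken from the stored preoperative data, provided the definition is fixed before the analysis. The statistical price is the 0.01 to 0.02 of power given above, and it is paid only if fracture pattern turns out to explain nothing.

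### The primary ORIF-time model names no factor for the number of sites to be plated, and allocation does not balance it, so in 50 patients precision is lost and a chance imbalance would go uncorrected

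*Combined protocol and SAP*

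**What the plan says.** - **Allocation (Study Design).** "Randomization will be performed by having sealed envelopes at the time of enrollment with either" of the two arm names on the card. The trial is described as non-blinded. No section mentions strata, blocks or minimisation.
- **Ratio and size.** General Information: "They will be split evenly into 2 groups which are virtual surgical planning (VSP) and the conventional surgery". Study Population: "We anticipate recruitment of approximately 50 patients (25 patients for each control and treatment group".
- **Eligibility (Study Population).** "Complex mandible fracture (at least two fractures) that require ORIF of at least one fracture". There is no upper limit, so the number of sites fixed runs from one upwards.
- **Primary endpoint (Objectives; Study Procedures).** "ORIF time will be defined as starting after the dissection is complete and fractures are reduced until final screws are placed". It is a single time per patient, not a time per fracture or per plate.
- **Case mix.** Background Information: "Treatment and surgical approaches vary with fracture patterns, location, degree of bony displacement, and involvement of dental structures". The Objectives table adds: "Age, gender, and fracture pattern is basic data needed to analyze results". Fracture pattern is on the data-collection list, and a secondary objective looks at other variables that may affect the result.
- **Analysis (Statistics).** "Generalized linear model will be used to identify data distribution differences between the two study groups". No covariate, distribution or link is given.

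**The concern.** A clock that stops at the last screw probably runs longer when more sites are fixed. The number of sites is therefore a likely predictor of the primary endpoint, and it can be judged before allocation: both arms have a medical-grade CT, and screening already requires counting the fractures and deciding that at least one needs ORIF.

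The plan recognises that fracture pattern matters, but it neither balances the number of sites at allocation nor commits to adjusting for it. Two things are at stake. Variation due to the number of sites stays in the residual, so precision is lost. And if chance puts more multi-site patients in one arm, the estimate moves with them and no pre-specified analysis corrects it. A covariate chosen after the data are seen, in an open-label trial, would be easy to challenge.

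**Working it through.** **Inputs from the protocol.** 25 patients per arm, f = 0.4, power 0.8, significance level 0.05.

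**Assumptions (not in the documents).** Share p of patients with two or more sites to plate: 20% to 50%. Extra ORIF time g for those patients: 0.5, 1.0 or 1.5 SD, where SD means the spread among patients in the same site class and same arm. Cards are a shuffled stack of 25 and 25.

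**1. The plan's own figure.** For two groups d = 2f = 0.8. The normal approximation gives 25 per group. The exact F-test gives 25.5, hence 26. At 25 per group the noncentrality is 0.8² × 25/2 = 8.0, and exact power with 1 and 48 df is 0.791. The plan's 25 and 26 both reproduce.

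**2. How often the arms differ.** With K multi-site patients among 50, the number in the VSP arm is hypergeometric (50, K, 25).

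| Share multi-site | K | P(arms differ by 5 or more) | P(VSP has the excess) |
|---|---|---|---|
| 20% | 10 | 7% | 4% |
| 30% | 15 | 22% | 11% |
| 40% | 20 | 15% | 7% |
| 50% | 25 | 26% | 13% |

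The sequence is uneven because the difference has the same parity as K: at 20% and 40%, five or more means six or more.

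**3. Size of the shift.** A five-patient difference is 5/25 = 0.20 in proportion. With g = 1 the raw difference moves by 0.20 × 1 = 0.2 SD. The design effect must be put in the same units. At p = 0.5 the overall SD is √(1 + g²p(1−p)) = √1.25 = 1.118, so the design effect is 0.8 × 1.118 = 0.894. The ratio is 0.2/0.894 = 22%. Without fixing the imbalance at five, simulation at p = 30% to 50% puts the 95th percentile of the absolute shift at about 0.14, 0.25 and 0.34 overall SD for g = 0.5, 1.0 and 1.5. That is 17%, 32% and 43% of the 0.8 effect.

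**4. Consequence given a five-patient imbalance** (p = 0.5, g = 1, two-group test without the factor, by simulation). Power is about 58% if VSP has the extra cases and about 94% if control has them. With no true effect and the extra cases in control, the chance of falsely favouring VSP is about 7% instead of 2.5%. For g = 0.5 to 1.5, power with the excess in VSP runs from 69% to 49%.

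**5. Over all allocations.** The unadjusted test rejects a true null in 4.6% to 5.2% of simulated trials. The 0.791 in step 1 uses the overall SD, so it already averages over these imbalances.

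**6. With the factor in the model.** Noncentrality is 8 × (1 + g²p(1−p)), on 1 and 47 df. At p = 0.5:

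| g | Noncentrality, balanced | Power, balanced | Noncentrality, 5-patient imbalance (× 0.96) | Power |
|---|---|---|---|---|
| 0.5 | 8.5 | 81.5% | 8.16 | 79.9% |
| 1.0 | 10.0 | 87.2% | 9.6 | 85.9% |
| 1.5 | 12.5 | 93.4% | 12.0 | 92.4% |

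The 0.96 is 1 − 0.2², because arm and site class then correlate at 0.2. At p = 0.2 the balanced noncentralities are 8 × 1.04 = 8.32, 8 × 1.16 = 9.28 and 8 × 1.36 = 10.88, which give about 81%, 85% and 90%.

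**The case against.** The strongest reply is that simple 1:1 randomisation is valid. Step 5 confirms it: the error rate holds, and the planned power already allows for chance imbalance. A reader might infer from step 4 that the envelopes bias the comparison or inflate the false-positive rate. The documents do not support that. Those figures are conditional on one unlucky allocation, and the direction that costs power occurs in at most 13% of allocations over the range examined.

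A reader might also infer that the protocol commits to an unadjusted test. It does not. It names a model without listing covariates, while calling fracture pattern necessary for the analysis. What stands is the lack of any pre-specified adjustment for the primary comparison.

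Third, stratified envelopes might seem to be the essential remedy. Step 6 shows otherwise: once the factor is in the model, perfect balance adds only 1 to 2 percentage points of power, even compared with a five-patient imbalance.

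Finally, the link between sites and time is inferred. The clock starts after dissection and reduction, which removes some site-dependent time, and General Information speaks of a single reconstruction plate. At g = 0.5 the gain is small. This limits the size of the point but does not remove it: the endpoint still ends at the final screws, and an adjustment that turns out weak costs one degree of freedom.

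**Conclusion.** The point holds as a gap in efficiency and pre-specification, not as a flaw in validity. If 20% to 50% of patients are multi-site, an imbalance of five or more arises in about 7% to 26% of allocations, half of these in each direction. If multi-site surgery adds 1 SD, an imbalance of five moves the raw difference by about 22% of the design effect. Adjusting for the factor removes the part of that shift due to site class. With half the patients multi-site, it raises power from 79% to about 81%, 87% or 93% for an added 0.5, 1.0 or 1.5 SD. The gain is smaller when fewer patients are multi-site. All of this rests on a share and an added time that the documents do not give. The change is worth making because the trial is small, exact power is just under its target, and the remedy is nearly free.

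**What to change.** 1. Add a line to the enrolment form for the planned number of ORIF sites (one, or two or more), completed from the preoperative CT before the envelope is opened. Use the planned number, not the number actually plated, because the latter is settled after allocation in an open-label trial.
2. State in the Statistics section that the primary model for ORIF time contains treatment arm and this two-level factor, and that the adjusted arm difference is the primary result.
3. Optionally, keep two envelope sets, one per level, each randomised 1:1 in permuted blocks of varying, undisclosed size. This adds little power beyond step 2 but prevents a visible imbalance.

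The cost is a short amendment, one form entry, one model term and, if step 3 is taken, a second set of envelopes. No extra patients or procedures are needed. The downside is that the planned number of sites must be settled before allocation, which the eligibility check does not fully require at present.
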